2.1 Primary Objectives

To investigate the efficacy of using FDA-approved doses of TD buprenorphine in combination with oral tramadol to provide adequate pain control in radiation-induced mucositis.

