As noted earlier, radiation-induced mucositis begins to heal approximately two weeks after the last dose of stomatotoxic chemotherapy or radiation therapy.(30, 32) Hence, we will assess a percentage drop in pain score by the end of week 9 of treatment to show a drug response. This way we will be able to avoid any bias of the normal healing process on pain alleviation. Studies have also shown that painful mucositis continues four to five weeks after the termination of radiation therapy. Thus, we plan to continue the study drug regimen up to 12 weeks. (17) (32) Recording of data will cease after 12 weeks, at which time mucositis-related pain symptoms substantially abate in many individuals. Details on buprenorphine and tramadol dose determination and titration are included in Section 5.2 of this protocol. Post-marketing data of buprenorphine, other opioid studies, and clinical experience have shown that around 20 percent of the patients receiving transdermal buprenorphine may have inadequate pain control and require rescue off-protocol pain medications despite being on the highest titratable dose of buprenorphine. Therefore, we have allowed the use of oxycodone in situations where pain is uncontrolled on highest titratable doses of the drug regimen and plan to monitor the use off-protocol pain oxycodone in our study.(17, 34)

Details for the use and logistics of the OM Pain App, as well as the measure of the patient's compliance to the use of the pain app are detailed below. This study will not interfere with or cause adjustments to the standard-of-care treatments each patient will receive as determined by their multidisciplinary team of cancer doctors. To this end, basic treatment descriptions and standards are briefly described as a reference to ensure proper patient selection and to verify that patients observed on the trial will be somewhat homogeneous from a treatment perspective. A short description of possible supportive treatments that could be needed during treatment is also included. All study interventions and treatments will be administered on an outpatient basis.

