5.2 Dose Determination for Buprenorphine and Tramadol

Based on our clinical experience and earlier studies barring exceptions, the typical MEDD dose of standard-of-care regimens, such as oxycodone, morphine and fentanyl patch used in the treatment of radiation-induced mucositis can range from 20 to 90 mg. Buprenorphine is a potent opioid substitute but there is no consensus at equipotency ratio for morphine to transdermal buprenorphine. Some authors have reported that it lies somewhere between 75:1 to 100:1.(34) This makes finding the appropriate morphine equivalent daily dose (MEDD) for buprenorphine in controlling mucositis-related pain a challenging task. For our study, we used 75:1 equipotency ratio to calculate our morphine equivalent daily dose (**Table 1**). As transdermal buprenorphine is a long-acting medication, we plan to allow tramadol 50 mg (total daily dose) as needed for breakthrough pain up to 400 mg/day (total daily dose), which roughly translates to 5 mg to 40 mg MEDD. Steady-state plasma buprenorphine concentration levels are achieved by day 3, during the first application of buprenorphine. Therefore, it can be titrated after a minimum of 72 hours. We hope to evaluate the possibility of using tramadol to facilitate dose adjustment of buprenorphine. With the buprenorphine and tramadol combination, we hope to provide MEDD to patients which is comparable to other standard-of-care opioids. There is no clear consensus definition of adequate and inadequate pain relief in this setting. However, it is well known that a VAS pain score of $\leq 3/10$ is considered mild intensity pain in multiple settings. Based on some earlier studies and the titratability of TD buprenorphine dose, we have defined adequate analgesia as VAS $\leq 3/10$ for 72 hours, inadequate analgesia as VAS $> 3/10$ for 72 hours, and unbearable pain as VAS $> 3/10$ for 96 hours.(16, 17) If patients have unbearable pain (VAS $> 3/10$ x 96 hours) despite being on highest dose of the buprenorphine patch and tramadol, then, we will switch from tramadol to oxycodone for breakthrough pain and continue treatment with buprenorphine. We will titrate this combination as needed for pain control until study completion. Some authors have also shown the benefit and safety of using immediate-release oxycodone in conjunction with transdermal buprenorphine for moderate to severe pain.(35) If the pain is still uncontrolled $> 3/10$ for 72 hours, even after using oxycodone 90 mg/day with buprenorphine 20 μ g/hour, then, the patient will be taken off the study regimen. However, data monitoring will continue. Patients suffering intolerable side effects (severe constipation, vomiting, headache, pruritis, sedation, or respiratory depression, etc.) or those who wish to switch to standard-of-care oxycodone due to ineffective pain control or unclear reasons at any time during the study will be taken off study regimen. However, data monitoring through the pain app and questionnaires will continue. The dose titration schedule is illustrated in **Table 2**.

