8.3 Study populations

- The enrolled population will consist of all enrolled patients. This population will be used in the CONSORT diagram, and patient disposition summaries.
- The treated population will consist of all enrolled patients who received at least one dose of the study medication. This population will be used for the efficacy and safety analyses.
- The per-protocol population will consist of all treated patients whose treatment followed without major protocol violations. This population will be used for sensitivity analyses.

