8.4 Determination of Sample Size and Accrual Rate

Based on earlier studies (48) and the IMMPACT recommendations(28), a 30% or higher decrease in pain score from baseline to the end of the follow-up period is a sign of clinically meaningful efficacy of the drug regimen within a patient. A randomized trial of pregabalin for the treatment of radiotherapy-related pain in head-and-neck cancer patients (33) observed an at least 30% decrease in 33% of placebo-treated patients. This study will use a single-stage design to evaluate the hypothesis that patients treated with buprenorphine will achieve at least a 30% decrease in pain with probability exceeding 33%. Formally, the following hypotheses will be evaluated at a one-sided 5% significance level:

$$H_0: p (\geq 30\% \text{ decrease}) = 0.33 \quad \text{versus} \quad H_a: p (\geq 30\% \text{ decrease}) > 0.33.$$

With 18 subjects, the study will have at least 80% power to reject the null hypothesis if the probability of achieving at least 30% decrease in pain with buprenorphine is, in fact, 63%. The hypothesized effect is consistent with the efficacy seen with other active treatments. Specifically,

buprenorphine will be considered an acceptable pain control medication if 10 or more subjects out of the 18 experience at least 30% pain reduction. We will enroll 20 subjects to allow for 10% drop-out rate.

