8.6 Data Analysis

Serial measurements of patient-reported pain data will be analyzed throughout the follow-up period to look for inadequate pain control and use of off-protocol breakthrough pain medication use. The pain app data will be analyzed by study coordinators and our collaborators at UWM. Data recording will commence on the day the patient starts taking the drug regimen. We plan to study the daily and weekly pain score patterns during therapy. We will determine the baseline VAS pain score on the day of treatment initiation. Other pain management studies in radiation-induced mucositis acknowledged the fact that the pain curve follows a nonlinear pattern during radiation therapy, but it plateaus and later drops down to a lower level after initiation of long-acting effective pain medications. Hence, it is reasonable to use the pain score on the day of treatment initiation as our baseline pain score. (29, 31) Radiation-induced mucositis begins to heal approximately two weeks after the last dose of stomatotoxic chemotherapy or radiation therapy.(30, 32) We will assess a percentage drop in the pain score by the end of week 9 of treatment to show a drug response. This way, we will try to avoid any bias of the normal healing process on pain alleviation. At least two-week treatment with study drug regimen will be required in order to be considered evaluable for study endpoints. Earlier studies and consensus guidelines have shown that a 30% drop in average weekly pain score by end of the follow-up period is significant. (28). The recording of data will cease after 12 weeks, at which time mucositis-related pain symptoms substantially abate in many individuals. (32)

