The primary analysis will compare the proportion of patients achieving a 30% drop in pain scores to the null-hypothesis value of 33% at a one-sided 5% significance level using a binomial test. The number of patients using analgesic and non-analgesic medications, as well as the occurrence of adverse events, will be tabulated and presented as counts with percentages. The average weekly pain scores, MDASI-HN, and the PROMIS® measures will be reported with descriptive statistics (mean, standard deviation, median, and range). Patient level summaries of the pain score and PRO outcomes will be created by computing area under the curve (AUC) of weekly averages. Scatterplots will be used to explore their relationship which will be quantified by Spearman's correlation coefficient. Further correlational analysis will be done by linear regression and linear fixed models.

8.7 Rationale for not Having a Stopping Rule: This is a supportive care pilot study to determine

the efficacy of transdermal buprenorphine and oral tramadol drug combination in alleviating radiation-induced mucositis pain in head and neck cancer patients. These pain medications are FDA approved and have an established safety profile. In addition to the primary efficacy endpoint, we will be evaluating other secondary end points, such as real-time pain monitoring through the OM Pain App. This will continue, even if the study drug regimen is discontinued for lack of efficacy or some other unspecified reason. This would provide us invaluable pilot data for future studies in this setting. Moreover, we have made provisions for switching to standard-of-care pain medications, such as oral oxycodone in our study for patients who don't derive adequate pain relief from the study regimen. Hence, it is reasonable to exclude a formal stopping rule for this trial.

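### Two sections define the primary efficacy denominator differently, and counting week-9 response regardless of rescue opioids does not match a conclusion about buprenorphine plus tramadol

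*Combined protocol and SAP*

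**What the plan says.** **Population.** Section 8.3 defines the treated population as "all enrolled patients who received at least one dose of the study medication" and assigns it to the efficacy and safety analyses. Section 8.6 adds a different condition: "At least two-week treatment with study drug regimen will be required in order to be considered evaluable for study endpoints". The per-protocol set in 8.3 depends on major protocol violations and is for sensitivity analyses only. Section 4.11 says treated patients who later withdraw are not replaced. Section 8.8 handles missing data by multiple imputation under missing at random (MAR).

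**Test and cut-off.** Section 8.6: "The primary analysis will compare the proportion of patients achieving a 30% drop in pain scores to the null-hypothesis value of 33" per cent, one-sided 5%, binomial test. Section 8.4: "buprenorphine will be considered an acceptable pain control medication if 10 or more subjects out of the 18" respond, with 20 enrolled to allow for 10% drop-out.

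**Response and rescue.** Sections 2.4 and 8.1.1 define response as a fall of at least 30% in pain from treatment start to the end of week 9, and 2.4 specifies the worst-pain item of the BPI. Rescue is not mentioned. Section 2.1 states the objective as "efficacy of using FDA-approved doses of TD buprenorphine in combination with oral tramadol". Section 5.1 expects about 20% to need rescue and says the investigators "plan to monitor the use off-protocol pain oxycodone in our study". Section 5.2, on patch plus oxycodone, says: "We will titrate this combination as needed for pain control until study completion". Section 5.4 lists oxycodone as a step in Table 2 and then allows patch removal with stronger opioids. Sections 4.11 and 5.2 keep collecting data after the regimen stops. Section 8.7 says of app-based monitoring: "This will continue, even if the study drug regimen is discontinued for lack of efficacy or some other unspecified reason".

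**The concern.** The two population rules part exactly where it matters. Under section 5.2 a patient can leave the regimen at any time for ineffective pain control or intolerable side effects. If that happens within two weeks, 8.3 keeps the patient in the efficacy denominator and 8.6 removes the patient. Those removed are not a random subset. In a small, open-label, single-arm trial with an exact cut-off, the choice should not remain open once results can be seen.

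The second issue is what a positive result would mean. Because scores continue after a switch, a patient whose pain was not controlled on buprenorphine plus tramadol, and who improved on oxycodone or a stronger opioid, can be a responder. The conclusion would then describe a strategy that includes rescue, while the objective names the combination. Rescue use is a secondary endpoint and will be tabulated, but nothing commits the report to showing how many responders were rescued.

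**Working it through.** **Inputs.** From 8.4: null 0.33, alternative 0.63, one-sided 5%, n = 18, success at 10 or more, 20 enrolled. From 5.1: about 20% needing rescue. Assumed, because the documents give no figure: that 20 are treated, that two stop before two weeks, and that such patients respond at 0% to 80%. All tail probabilities are exact binomial, P(X ≥ r | n, p).

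**1. The plan's own figures.** P(X ≥ 10 | 18, 0.33) = 0.0405 and P(X ≥ 10 | 18, 0.63) = 0.8165. The stated 80% power and the cut-off of 10 reproduce; 9 of 18 would give p = 0.1019. The sample-size arithmetic is sound.

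**2. Same responders, different denominator.**

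| Result | One-sided p at 0.33 |
|---|---|
| 10 of 18 | 0.0405 |
| 10 of 20 | 0.0866 |
| 11 of 20 | 0.0350 |

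Ten responders are positive under the two-week rule with 18 evaluable. They are not positive under the one-dose rule with 20 treated, provided neither excluded patient responds.

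**3. Effect of dropping early stoppers.** Let 20 be treated with a true response rate of 33%, so 0.33 × 20 = 6.6 expected responders. Two stop early and respond at rate e. The rate among the remaining 18 is (6.6 − 2e)/18.

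| e | Rate in the 18 | P(≥ 10 of 18) |
|---|---|---|
| 0 | 0.3667 | 8.0% |
| 0.25 | 0.3389 | 4.8% |
| 0.33 | 0.3300 | 4.1% |
| 0.80 | 0.2778 | 1.2% |

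The 8.0% is an upper bound: it requires that neither early stopper would respond. If their response rate exceeds 33%, dropping them lowers the chance of a positive result.

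**4. Cut-offs for the n that may occur.**

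| n | Cut-off | Exact alpha | Power at 0.63 |
|---|---|---|---|
| 18 | 10 | 4.1% | 81.6% |
| 19 | 11 | 2.2% | 76.0% |
| 20 | 11 | 3.5% | 83.5% |

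The plan gives only the first row. Applying 10 to n = 19 or n = 20 would give alpha of 6.1% or 8.7%.

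**5. Does the two-week rule deal with rescue?** In Table 2, oxycodone follows five 72-hour steps and one 96-hour step: 5 × 72 + 96 = 456 hours, or 19 days. Patch removal comes 72 hours later: 528 hours, or 22 days. Patients who follow the schedule are therefore evaluable when rescued. At 20%, the expected number is 0.20 × 18 = 3.6.

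**6. Cost of making rescue-as-failure the primary rule.** Assume that 63% applies only to patients without rescue. With 10% rescued the rate is 0.63 × 0.90 = 0.567 and power at 10 of 18 is 63.5%. With 20% rescued it is 0.63 × 0.80 = 0.504 and power is 42.1%.

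**The case against.** **The plan already has a rescue rule.** A reader might infer that the plan cannot classify rescued patients at all. The documents do not support that. Response is defined by score alone, efficacy uses all treated patients, and scores continue after discontinuation; read literally, patients count regardless of rescue. What stands is that the rule is implicit and does not match a conclusion about the combination. Nor is every rescued patient clearly a failure of the study drug: 8.4 judges buprenorphine, and 5.2 and 5.4 build patch plus oxycodone into titration. The mismatch is clearest for patients off the patch. The sentence quoted from 8.7 concerns secondary monitoring and is weak evidence for the primary score; 5.2 carries that point.

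**The type I error is not inflated by rescue.** A reader might also infer that rescue pushes the error rate far above 5%. With 20% rescued and an assumed 25% to 80% of them responding, P(≥ 10 of 18) runs from 2.9% to 18.6% if 33% of the non-rescued respond. It reaches 37.4% if rescued responders are added on top of 33% of everyone. These are not type I errors of the stated test, whose null concerns response in treated patients. If that rate is 33%, rejection is 4.1% however many were rescued. The figures only show how often a positive result could occur if rescue-free response were the target. The documents do not say whether the 33% placebo benchmark counted rescued patients.

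**Early stoppers may respond, and 20 is the enrolment figure.** Both points stand. Scores continue after stopping, so one responder among the two excluded gives 11 of 20 and p = 0.035. At response rates of 25% to 80%, at least one of two responds with probability 44% to 96% (1 − 0.75² and 1 − 0.20²). Treatment starts only when pain reaches the threshold, so drop-out could precede the first dose and leave about 18 treated.

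**Dependence on one patient is no defect.** Any exact cut-off at n = 18 has this property. It shows only why the denominator must be fixed in advance.

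**Conclusion.** The population conflict between 8.3 and 8.6 is certain from the text and should be fixed. It can reverse the conclusion at 10 responders. The effect on the chance of a positive result is modest and can go either way: at most 8.0%, against the planned 4.1%, if two of 20 treated patients stop early and neither would respond; between 4.8% and 1.2% if they respond at 25% to 80%. The number treated, the number stopping and their response rates are all assumptions.

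The rescue point is secondary. Counting response regardless of rescue is legitimate and is what the plan says when read literally. The fault is that it is not declared, the conclusion is worded more narrowly than the count, and no analysis shows how far success rests on other opioids in the roughly 20% expected to need them. The size of that effect cannot be settled from the documents. Sections 5.1 and 5.2/5.4 also differ on whether oxycodone lies outside the protocol, and must be reconciled before rescue can be defined.

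**What to change.** **Population (8.3, 8.6).** Make the at-least-one-dose population primary. Remove the two-week condition from the primary analysis, or keep it only for a sensitivity analysis.

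**Early stoppers (8.6, 8.8).** Use the observed week-9 score where there is one, since scores are still collected. Prespecify non-response for patients who stopped for lack of pain control or intolerance and have no week-9 score, in place of MAR imputation for them.

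**Cut-off (8.4).** State the exact cut-off for the actual n: 10 of 18, 11 of 19, 11 of 20.

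**Rescue (8.1.1, 8.6).** State that the primary count is regardless of rescue, and word the conclusion as the strategy including rescue. Prespecify a sensitivity analysis that counts as non-responders patients moved to another opioid for lack of pain control before the week-9 score. Show patch-plus-oxycodone and off-patch patients separately. Say how patients given intravenous opioids in hospital and then returned to the regimen are classified. State whether the 33% and 63% rates include rescued patients.

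**Consistency (5.1, 5.2, 5.4).** Reconcile the status of oxycodone. This is a labelling matter for the analysis and takes no position on treatment.

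**Cost.** Wording and slightly more analysis, using the diary, opioid log and prescription-monitoring data already collected. No extra patients and no change to care. With 20 treated, 11 of 20 keeps alpha at 3.5% and power at 83.5%; with 19, power is 76.0%, which should simply be stated. The conclusion becomes more exact about what was tested. Keeping rescue-as-failure as a sensitivity analysis avoids the power loss it could bring as the primary rule.

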4.11 Discontinuation of Study Treatment, Withdrawal, and Compliance

Discontinuation from the study treatment does not mean discontinuation from the study. The subject will be considered in follow-up, study procedures should still be completed as indicated by the study protocol, and AEs/SAEs will continue to be reported according to this protocol.

In the absence of treatment delays due to adverse events, study treatment/intervention may continue until:

- General or specific changes in the subject's condition renders the subject unacceptable for further treatment in the investigator's judgment.
- An inter-current illness that prevents further treatment administration.
- The subject decides to withdraw from the study.
- The subject has significant noncompliance with the protocol (see below).
- Unacceptable adverse event(s) and/or dose level reduction beyond requirements as detailed in this protocol.
- The clinical need for concomitant therapy that is not permitted in the study.
- Subjects who sign the informed consent form, enroll, and receive the study intervention, but subsequently withdraw, or are withdrawn or discontinued from the study will not be replaced.

Consent Withdrawal

A subject may decide to withdraw from the study at any time. MCWCC CTO will follow their IRB of record's SOPs regarding consent withdrawal.

If a subject intends on withdrawing consent, staff should confirm which of the following options the subject chooses and document the discussion:

- Full consent withdrawal, with no study follow-up.
- Selective consent withdrawal from the interventional portion of the study but agree to continued follow-up of associated clinical outcome information.

Investigator-initiated Withdrawal

The investigator will withdraw a subject whenever continued participation is no longer in the subject's best interests. Reasons for withdrawing a subject include, but are not limited to, disease progression, the occurrence of an adverse event or a concurrent illness, a subject's request to end participation, a subject's noncompliance, or simply significant uncertainty on the part of the investigator that continued participation is prudent. The reason for study withdrawal and the date the subject was removed from the study must be documented.

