5.4 Drug Regimen Titration Schedule

Table 2 Drug Titration Schedule

Drug: Buprenorphine with tramadol for breakthrough pain (**First seven weeks of study**) $T = 0 - 7$ weeks;

Start TD buprenorphine 5 μ g/hour along with oral tramadol 50 mg to 150 mg (total dose over 24 hours) as needed for breakthrough pain when mucositis related pain is $\geq 4/10$ on VAS measured on OM Pain App and BPI. Further dose adjustments will be made through pain app.

- If VAS is $>3/10$ for 72 hours on tramadol 150 mg (total dose over 24 hours) and buprenorphine 5 μ g/hour, then, increase tramadol to 250 mg (total dose over 24 hours).
- If VAS is $>3/10$ for 72 hours, even with tramadol 250 mg (total dose over 24 hours) and buprenorphine 5 μ g/hour, then, increase dose of buprenorphine to 10 μ g/hour.
- If the pain persists VAS $>3/10$ for 72 hours on tramadol 250 mg (total dose over 24 hours) and 10 μ g/hour, then, increase the dose of tramadol to 350 mg (total dose over 24 hours).
- If VAS pain is $>3/10 \times 72$ hours with both tramadol 350 mg (total dose over 24 hours) and buprenorphine 10 μ g/hour, then, increase dose of buprenorphine to 15 μ g/hour.
- If VAS pain $>3/10 \times 72$ hours on tramadol 350 mg (total dose over 24 hours) and 15 μ g/hour of buprenorphine, then, increase the dose of tramadol to 400 mg (total dose over 24 hours) and buprenorphine to 20 μ g/hour.
- If the pain persists and is unbearable at $>3/10$ for 96 hours, despite being on highest dose of both drugs, then, replace tramadol with oxycodone at the clinician's discretion up to 90 mg (total dose over 24-hour period) for pain relief.
- If VAS is $\leq 3/10$ maintained for 72 hours, then, we can start tapering off total daily tramadol dose by 50 mg every day, but not change the buprenorphine dose during the first seven weeks of treatment, as mucosal injury from ongoing radiation may increase pain later.

(Post-radiation period) $T = 8 - 12$ weeks: if necessary, increase dose of buprenorphine up to 20 mcg along with tramadol up to 400 mg/day as per titration schedule used in the first seven weeks until VAS is $\leq 3/10$. If pain is well controlled (VAS $\leq 3/10 \times 72$ hours), start weekly tapering of buprenorphine by 5 mcg and tramadol by 50 mg daily.

Special Circumstances

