If pain is uncontrolled with VAS $>3/10 \times 72$ hours on 90 mg oxycodone (total dose over 24-hour period) and 20 μ g/hour of buprenorphine, then, buprenorphine patch can be taken off and other stronger pain medications can be started at clinician's discretion. If the patient is admitted and requires IV pain medication for pain control, then, the study drug regimen will be held, and data monitoring will stop for that time. The patient can be discharged on the study regimen (tramadol and buprenorphine) or a combination of oxycodone and buprenorphine patch or any other combination at clinician's discretion, and data monitoring will resume.

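### The week 9 responder definition has no rule for patients taken off buprenorphine, so relief on a replacement opioid counts toward the 10-of-18 success rule

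*Combined protocol and SAP*

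**What the plan says.** The primary analysis in 8.6 reads: "The primary analysis will compare the proportion of patients achieving a 30% drop in pain scores to the null-hypothesis value of 33"%, by a one-sided 5% binomial test. Sections 2.4 and 8.1.1 define response as a drop of at least 30% from the score at treatment start to the end of week 9. Section 8.3 bases efficacy on every patient who took at least one dose. Section 8.6 adds that two weeks on the regimen are needed to be evaluable. Section 8.4 calls buprenorphine acceptable if at least 10 of 18 respond.

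The protocol provides several ways off buprenorphine, all with continued data collection:

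- Section 5.2, pain uncontrolled on oxycodone 90 mg/day plus the 20 µg/hour patch: "then, the patient will be taken off the study regimen. However, data monitoring will continue". The same applies to patients with intolerable side effects and to "those who wish to switch to standard-of-care oxycodone due to ineffective pain control".
- Section 5.4, same clinical situation: "then, buprenorphine patch can be taken off and other stronger pain medications can be started at clinician's discretion".
- Section 5.4, discharge after IV analgesia, on the study drugs, on oxycodone with the patch, "or any other combination at clinician's discretion, and data monitoring will resume".
- Section 4.11 lists among the reasons to end study treatment: "The clinical need for concomitant therapy that is not permitted in the study". It also states: "Discontinuation from the study treatment does not mean discontinuation from the study. The subject will be considered in follow-up".

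A different step keeps the patch on. At maximum doses with persisting pain, Table 2 in 5.4 says to "replace tramadol with oxycodone at the clinician's discretion up to 90 mg" per 24 hours.

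**The concern.** The objective in 2.1 is the efficacy of transdermal buprenorphine with tramadol. If that regimen failed a patient or could not be tolerated, and the patient is comfortable at week 9 on an opioid regimen without buprenorphine, the score says little about buprenorphine. Section 8.7 describes the switch to standard opioids as a provision for patients who get too little relief from the study regimen. The care plan thus treats these patients as failures of the regimen, while the primary count can record them as successes.

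There is no control arm in which the same switching would occur, and the decision rests on a count in 18 patients. One or two classifications can settle it.

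**Working it through.** **1. Is there a rule anywhere?** Sections 8.1.1, 8.3, 8.4 and 8.6 do not mention a change of opioid. The two-week condition in 8.6 concerns time on the regimen. Section 8.8 imputes missing scores, but a switched patient's score is normally observed. The per-protocol set in 8.3 is for sensitivity only, leaves major violations undefined, and the protocol itself permits these switches. Secondary endpoint 2 and the medication tabulation in 8.6 make off-protocol opioid use visible but do not alter the 10-of-18 decision.

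**2. Can it happen in time?** Table 2 needs five 72-hour steps and then 96 hours to reach oxycodone: 5 × 72 + 96 = 456 h = 19 days. A further 72 h leads to patch removal: 528 h = 22 days. Section 3.2 expects most patients to start by week 4. A start on days 22–28 puts the earliest patch removal for pain on days 44–50. That is past two weeks on treatment and before the end of week 9 (day 63). Removal for side effects, or a switch on request, can come sooner.

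**3. The plan's own figures reproduce.** Inputs from 8.4: n = 18, null rate 0.33, alternative 0.63, success at 10 or more.

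- P(Bin(18, 0.33) ≥ 10) = 0.0405
- P(Bin(18, 0.33) ≥ 9) = 0.1019
- P(Bin(18, 0.63) ≥ 10) = 0.8165

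The cut-off of 10 is right and power exceeds 80%. If exactly 10 respond, reclassifying one of them moves p from 0.041 to 0.102.

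**4. Chance of declaring success when scores after leaving buprenorphine count.** Let m patients have left buprenorphine and respond at rate r, while the other 18 − m respond at 0.33. Then X = Bin(18 − m, 0.33) + Bin(m, r), and the table gives P(X ≥ 10). Both m and r are assumptions, because the documents give neither.

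| r | m = 1 | m = 2 | m = 3 | m = 4 |
|---|---|---|---|---|
| 0.20 | 3.5% | 2.9% | 2.5% | 2.1% |
| 0.33 | 4.1% | 4.1% | 4.1% | 4.1% |
| 0.45 | 4.6% | 5.2% | 5.9% | 6.6% |
| 0.63 | 5.4% | 7.2% | 9.4% | 12.0% |

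The value passes 5% once r reaches about 54%, 43%, 40% or 38% for m = 1, 2, 3 or 4.

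**5. Power if such patients count as non-responders.** With the others at 0.63, power is P(Bin(18 − m, 0.63) ≥ 10): 81.6% for m = 0, 73.2% for m = 1, 62.5% for m = 2, 49.9% for m = 3 and 36.2% for m = 4.

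**The case against.** **The percentages are not type I error rates under the stated hypothesis.** This stands. The null in 8.4 is a 33% chance of a 30% decrease and does not mention rescue. With 14 patients at 33% and 4 at 63%, the average rate is (14 × 0.33 + 4 × 0.63)/18 = 0.397, so that null is false and 12.0% is a chance of success against it. A reader might infer that the trial's error rate is inflated to 12%. The documents do not support that. The figures are errors only if the question is what the regimen achieves by itself, and 8.4 does not define the null that way.

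**The direction is unknown.** This also stands. Patients who failed maximum doses may do worse than 33%, and the chance of success then falls.

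**The 20% in 5.1 is not a rate of leaving buprenorphine.** A reader might take it to mean that 3.6 of 18 patients will be counted on a replacement drug alone. Section 5.1 uses the figure to justify oxycodone at the highest study doses, and 5.2 says buprenorphine continues at that step. These patients follow a planned titration with the patch on, so their relief cannot be assigned to the other opioid alone.

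**The default is read from silence.** Section 5.1 speaks of patients being treated with the regimen and 8.4 of response with buprenorphine, which could mean scores on treatment only. But neither sentence sets a counting rule, and the treated population in 8.3 with continued data collection points the other way.

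**Counting all observed scores can be a legitimate choice.** It can, if stated. The plan does not state it, and it fits poorly with a conclusion about buprenorphine as an acceptable pain medication.

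**Conclusion.** The gap is real and should be fixed. As written, a patient taken off buprenorphine for uncontrolled pain or intolerable side effects can be one of the 10 successes because of relief on another opioid. That follows from the treated population, continued data collection and a responder definition based on the score alone. It needs no assumption about rates.

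The size does rest on assumptions. For 1 to 4 such patients and response rates from 20% to 63%, the chance of declaring success, with the others at 33%, runs from 2.1% to 12.0% against 4.1% for the plain design. What is certain is the sensitivity of the rule: a result at the cut-off turns on one classification.

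The finding does not extend to treating every patient on oxycodone with the patch as a regimen failure. The sample-size arithmetic in 8.4 is correct.

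**What to change.** Add to 8.6: a patient who, before the end of week 9, permanently stops the buprenorphine patch for inadequate pain control or intolerable side effects, or is switched to an opioid regimen without buprenorphine, counts as a non-responder in the primary analysis. The observed week 9 score in all treated patients is a sensitivity analysis.

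Add for patients taking oxycodone with the patch still on: the observed score counts in the primary analysis, and a prespecified sensitivity analysis counts them as non-responders. Making failure coding primary for this group would be expensive. At the 20% in 5.1, 3 or 4 patients would be affected, and power would be 49.9% or 36.2% with the others at 63%.

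State in 8.4 whether the 63% is already net of patients who leave the regimen. If it is, power is unchanged. If it is not, power falls from 81.6% to 73.2% with one such patient and 62.5% with two, and the protocol should say so. For a pilot, keeping 20 patients and stating the lower power is reasonable.

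The cost is amendment wording in 8.6 and 8.4, and case report form fields for the date and reason the patch was stopped and the analgesic in use at week 9. No new visits or procedures are needed, and prescribing under 5.4 need not change. The rule should be fixed before the week 9 data are seen.
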